Exclusion Criteria

In accordance with Absolute and Relative Contraindications for use for Vanguard Complete Knee System and Vanguard High Flex Rotating Platform Knee System.

Absolute contraindications include: infection, sepsis, osteomyelitis, and failure of a previous joint replacement.

Relative contraindications include:

- A. Uncooperative patient or patient with neurologic disorders who are incapable of following directions,
- B. Osteoporosis,
- C. Metabolic disorders which may impair bone formation,
- D. Osteomalacia,
- E. Distant foci of infections which may spread to the implant site,
- F. Rapid joint destruction, marked bone loss or bone resorption apparent on roentgenogram,
- G. Vascular insufficiency, muscular atrophy, neuromuscular disease,
- H. Incomplete or deficient soft tissue surrounding the knee.

ENDPOINTS

	SUBGROUP 2	SUBGROUP 4
PRIMARY ENDPOINTS*	Range of Motion at 1 yr postop. AKS at 1 year postop	Range of Motion at 1 yr postop. AKS at 1 year post op
SECONDARY ENDPOINTS	At all follow-up visits: Survivorship American Knee Society Score. Range of Motion Radiographic Assessment Patient Satisfaction – EQ5D Complications including revisions Patella Clunk and Crepitus	At all follow-up visits: Survivorship American Knee Society Score. Range of Motion Radiographic Assessment Patient Satisfaction – EQ5D - OKS - FJS Complications including revisions Patella Clunk and Crepitus

*For sample size calculations.

PARTICIPANT POPULATION (SAMPLE SIZE)

Participant population is determined based on primary/secondary endpoints of each subgroup following superiority or non-inferiority methodologies. Minimum sample sizes are determined in order to prove the hypotheses.

Subgroup 2 - Primary Endpoint Range of Motion at 1 year postoperative
 Superiority test

Null Hypothesis: H_0 $\mu_t = \mu_c$

Alternative Hypothesis: H_a $\mu_t = \mu_c + d$

μ_t : mean of ROM in the trial group (Vanguard Complete Knee) at 1 year postoperative.

μ_c : mean of ROM in the control group (VG RP Knee) at 1 year postoperative.

$\alpha = 0.025$ Significance Level (95% confidence)

$\beta = 0.20$ 80% Power

$d = 5$ (degrees) Clinically Relevant Difference in ROM based on literature and engineering input.

$\xi = 17.5$ Estimate standard deviation of ROM at 1 year postoperative. This value is based on results (preop and 1 year postop) from literature¹

$N = 231$

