Consider lost to follow-up at 1 year postop, therefore the adjusted sample size is set as **250 knees per group (a total of 500 knees)**.

Subgroup 2 - Secondary Endpoint AKS at 1 year postoperative
 Non-inferiority test

Null Hypothesis: H_0 $\mu_t = \mu_c$

Alternative Hypothesis: H_a $\mu_t = \mu_c + d$

μ_t : mean of AKS score in the trial group (Vanguard Complete Knee) at 1 year postoperative.

μ_c : mean of AKS score the control group (VG RP Knee) at 1 year postoperative.

¹ [Miner AL](#), [Lingard EA](#), [Wright EA](#), [Sledge CB](#), [Katz JN](#); Knee range of motion after total knee arthroplasty: how important is this as an outcome measure, *J Arthroplasty*. 2003 Apr;18(3):286-94.

$\alpha = 0.025$	Significance Level (95% confidence)
$\beta = 0.10$	80% Power
$Z_{1-\alpha/2} = 1.96$	
$Z_{1-\beta} = 1.28$	
$d = 10$ points	Clinically Relevant Difference in Pain.
$\xi = 15$	Estimate standard deviation of AKS at 1 year postoperative. This value has been based on results from Biomet studies
$N = 48$	
	Consider possible lost to follow-up at 1 year postop, therefore the adjusted sample size is set as 51 knees per group. The final sample size for subgroup 2 is larger of the two sample sizes: 250 knees per group.
	Therefore there will be 250 Vanguard Complete Knee will be compared to 250 Vanguard High Flex RP knee for subgroup 2 study.
	Due to unknown release schedule for new designed VG High Flex RP Knee, sample size of subgroup 4 will be determined at time of the product release. Nevertheless the sample size will be determined based on the comparison to results of 250 VG High Flex RP knee of current design from subgroup 2.

RANDOMIZATION

For subgroup 2 study, patients will be randomized to receive Vanguard Complete Knee (trial group), or Vanguard High Flex RP Knee (control group). Patients have an equal opportunity of being assigned to the trial group or control group. The randomization will occur via a random number generator (manual or computer). The doctor or other health care professional does not choose the participants for each group. For Patients satisfying inclusion criteria, randomization will occur by retrieving the next randomly generated group assignment.

INSTITUTIONS

There will be a maximum of 8 sites from Korea and Japan in subgroup 2. The number of sites for subgroup 4 will be determined once new design of Vanguard High Flex RP is released.

PARTICIPANT DATA MANAGEMENT

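### Subgroup 2: 1-year AKS is primary in the Endpoints table but secondary in the sample-size section, and no rule says which result decides the comparison

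*Combined protocol and SAP*

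**What the plan says.** All of the text is in the combined protocol and SAP.

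- **Endpoints table, primary row, subgroup 2:** "Range of Motion at 1 yr postop. AKS at 1 year postop". Both variables stand there without ranking. The row's footnote reads "For sample size calculations". The secondary row lists AKS and ROM again for every follow-up visit, which includes 1 year.
- **Participant Population (Sample Size), opening:** "Participant population is determined based on primary/secondary endpoints of each subgroup following superiority or non-inferiority methodologies".
- **Same section, first calculation:** "Subgroup 2 - Primary Endpoint Range of Motion at 1 year postoperative", described as a "Superiority test". Inputs are alpha 0.025, beta 0.20, a difference of 5 degrees and SD 17.5, giving N = 231.
- **Same section, second calculation:** "Subgroup 2 - Secondary Endpoint AKS at 1 year postoperative", described as a non-inferiority test. Inputs are alpha 0.025, critical value 1.96, beta 0.10 with Z = 1.28, d = 10 points and SD 15, giving N = 48.
- **Final size:** the larger of the two adjusted figures, 250 knees per group.

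The document has no analysis section, testing order, success criterion or multiplicity adjustment.

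**The concern.** One variable, at one time point, in one subgroup, has two statuses. The two tests also answer different questions: ROM asks whether one implant is better, AKS whether one is not materially worse. If the implants perform alike, the expected pattern is that ROM shows no difference and AKS passes. Under the sample-size section that pattern is a failed primary endpoint. Under the Endpoints table it could be reported as success on a primary endpoint.

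If the choice is left until the data are seen, the reported conclusion depends on which part of the plan is cited. Under an either-suffices rule, the chance of a false claim would also exceed the per-test level. The separate problems with the alpha and beta labels do not bear on this: correcting them would leave AKS both primary and secondary.

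**Working it through.** **1. The plan's own sizes.** Per-group n = 2[SD(z_alpha + z_beta)/d]².

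- AKS: 2[15(1.96 + 1.28)/10]² = 47.2, rounded up to 48. This matches the stated 48, at 90% power and z = 1.96.
- ROM with z = 1.96: 2[17.5(1.96 + 0.8416)/5]² = 192.3, so 193. This does not match 231.
- ROM with two-sided 0.025 (z = 2.2414): 2[17.5(2.2414 + 0.8416)/5]² = 232.9, so 233. This is close to 231.

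The two calculations therefore appear to use different alpha conventions, and neither states its sidedness.

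**2. Chance that AKS passes when the implants are equal.** Inputs are 231 evaluable knees per arm, SD 15, true difference zero, and d = 10 taken as the margin.

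- Standard error = 15 × √(2/231) = 1.396.
- 10/1.396 = 7.165, and 7.165 − 1.96 = 5.205.
- Φ(5.205) > 0.9999.

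**3. The three possible decision rules when ROM shows no difference and AKS passes.**

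| Rule | Textual basis | Result | Error above the per-test alpha? |
|---|---|---|---|
| ROM alone | Sample-size section | Failure | No |
| Both required | One reading of the Endpoints table | Failure | No |
| Either suffices | Another reading of the Endpoints table | Success | Yes |

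**4. Family-wise error if either suffices, at the stated 0.025 each.** The null is equal ROM and a true AKS deficit exactly at the 10-point margin.

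- Upper bound: 0.025 + 0.025 = 0.05.
- Independent: 1 − 0.975² = 0.0494.
- Correlated endpoints, bivariate normal: at 0.5, 4.5% with both tests one-sided or 4.6% with both two-sided; at 0.7, 4.2% or 4.3%. The correlations are assumptions, since the document gives none. Independence is unlikely, because the data-collection table records ROM as part of the AKS assessment.

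**5. Power under a strict rule.** At 231 per arm the ROM standard error is 17.5 × √(2/231) = 1.628, and 5/1.628 = 3.071.

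- ROM power at two-sided 0.05: Φ(3.071 − 1.96) = 87%.
- ROM power at two-sided 0.025: Φ(3.071 − 2.2414) = 80%.

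AKS fails with negligible probability under step 2, so the probability that both succeed is about the ROM power.

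**The case against.** **The footnote might settle it.** It ties the primary label to sample-size work, so one could say the sample-size section governs. That does not resolve the conflict, because the calculation it points to is where AKS is called secondary. Taking the larger N sets the size of the trial, not the result that decides it.

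**A reader might infer that the false-positive rate is simply uncontrolled.** The document does not support that. Inflation needs the either-suffices rule, which is stated nowhere. Even then the stated 0.025 per test caps the total at 5%: double a one-sided 0.025 target, but equal to an overall 0.05.

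**A reader might also quote 9.75%, from 1 − 0.95².** That needs two-sided 0.05 on each test. The 95% confidence label and the 1.96 make it conceivable, but the stated alpha is 0.025. Two-sided 0.05 also fits poorly with a non-inferiority test, where only one direction counts as success.

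**The null matters.** If the implants are truly equal on both measures, declaring AKS non-inferior is correct and the only possible error is on ROM. This stands, and the figures in step 4 carry that condition. The AKS hypotheses are written in superiority form, so reading d as a margin relies on the non-inferiority label.

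**Perhaps alpha was already split.** N = 231 nearly fits two-sided 0.025, as if 0.05 had been shared between two endpoints. The document never says so, and the AKS calculation uses 1.96.

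**AKS might deserve primary status.** The study objectives name clinical outcomes alongside early ROM, so making ROM the sole primary is a choice and does not follow from the text. This also stands, and requiring both endpoints would be acceptable.

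**Conclusion.** The concern holds for subgroup 2. The status of 1-year AKS is contradictory, and no decision or multiplicity rule says whether ROM, both or either decides the comparison. The main consequence is that one dataset could be read as success or failure. When the implants are truly equal, AKS passes with probability above 99.9%, assuming 231 evaluable knees per arm, SD 15 and a 10-point margin.

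The effect on error is conditional. It is at most 5% at the stated 0.025 each, 4.9% if independent and about 4.2–4.6% at assumed correlations of 0.7–0.5. This applies only if either endpoint suffices and the true AKS deficit lies at the margin.

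A reader might extend the contradiction to subgroup 4. Its primary row also lists both endpoints, but its sample size is deferred and no section calls its 1-year AKS secondary. Only the missing decision rule carries over.

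This should be settled before outcome data are examined, because it determines what the randomised comparison can claim.

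**What to change.** Give 1-year AKS the same status in the Endpoints table and the sample-size section, and state the decision rule and the alpha with its sidedness.

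- **Simplest choice, consistent with the sample-size section:** ROM at 1 year is the single primary endpoint (superiority). AKS at 1 year is the key secondary, tested for non-inferiority at the same alpha only if ROM succeeds. AKS leaves the primary row.
- **Acceptable alternative:** keep both as primary and require both to succeed.

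Neither option needs an alpha adjustment. N stays at 250 per group, and the probability of succeeding on both remains about the ROM power. The cost is an amendment to the wording. The downside is that AKS cannot carry a claim on its own if ROM fails.

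For subgroup 4, set the same rule before its deferred sample size is calculated.

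### The 1-year AKS comparison is called a non-inferiority test but is written with superiority hypotheses, with no margin-based null or decision rule

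*Combined protocol and SAP*

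**What the plan says.** The section PARTICIPANT POPULATION (SAMPLE SIZE) opens by saying that sizes are set "following superiority or non-inferiority methodologies", and adds: "Minimum sample sizes are determined in order to prove the hypotheses". Two Subgroup 2 blocks follow.

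- **ROM at 1 year**, headed "Superiority test": equality of means as the null, and trial mean equal to control mean plus d as the alternative.
- **AKS at 1 year**, headed "Non-inferiority test": "Null Hypothesis: H_0 $\mu_t = \mu_c" against "Alternative Hypothesis: H_a $\mu_t = \mu_c + d", the same pair.

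In both blocks the trial group is Vanguard Complete and the control group is High Flex RP. The AKS inputs are alpha = 0.025, critical value 1.96, beta = 0.10, power quantile 1.28, d = 10 points and SD 15. They give N = 48 per group, raised to 51 for loss to follow-up. The 10 points are described as a "Clinically Relevant Difference in Pain", not as a margin. The block ends: "The final sample size for subgroup 2 is larger of the two sample sizes: 250 knees per group". The document has no statistical analysis section, and no other section gives a non-inferiority null, margin or criterion.

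**The concern.** A superiority test and a non-inferiority test cannot share one null and one alternative. The null of a non-inferiority test is that the trial arm is worse by at least a stated margin; equality is not that null. Rejecting equality in favour of the trial knee would show superiority, which implies non-inferiority, but a non-inferiority aim should not depend on showing superiority. Failing to reject equality shows neither, and the plan does not say how such a result would be read.

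The risk is that a non-significant difference gets reported as non-inferiority, or that a margin is chosen once the results are known. The endpoint is not peripheral: the ENDPOINTS table lists 1-year AKS as primary.

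**Working it through.** **Inputs.** From the AKS block: SD = 15, d = 10, critical value 1.96, power quantile 1.28, N = 48. From the ROM block: 231 per group before, and 250 after, allowance for loss to follow-up. The margin M is not in the documents. M = 10 is assumed first because d = 10; 7.5 and 5 are illustrative, as is the 3-point deficit in step 4.

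**1. Reproduce N.** n = 2 × (1.96 + 1.28)² × (15/10)² = 47.2, rounded up to 48. This is the size for a difference test with effect 10. It is also the size for a non-inferiority test with margin 10 and true difference 0, because the two formulas are then algebraically the same. N = 48 therefore cannot show which test was meant. Power at 48 per group is 90.4%. For 80% power the size would be 2 × (1.96 + 0.8416)² × (15/10)² = 35.3, so 36.

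**2. Standard error of the difference.** SE = 15 × √(2/n): 1.396 at n = 231 and 1.342 at n = 250.

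**3. Knees truly equal.** The written test rejects at its type I error rate: 2.5% one-sided (alpha = 0.025 with the +d alternative), or 5% if 1.96 is used two-sided. A non-inferiority test succeeds with probability Φ(M/SE − 1.96):

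| M (assumed) | n = 231 | n = 250 |
|---|---|---|
| 10 | >99.9% | >99.9% |
| 7.5 | 99.97% | 99.99% |
| 5 | 94.8% | 96.1% |

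**4. Trial knee truly 3 points worse.**

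- Written test, one-sided: Φ(−3/1.396 − 1.96) = 0.002% at 231; Φ(−3/1.342 − 1.96) = 0.001% at 250.
- Written test, if assumed two-sided, rejecting in the direction of worse: Φ(3/1.396 − 1.96) = 57.5% at 231; Φ(3/1.342 − 1.96) = 60.9% at 250.
- Non-inferiority at M = 10: Φ(7/1.396 − 1.96) = 99.9% at 231.

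The conclusion thus depends on which test is run, and on its sidedness.

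**5. Does 250 per group still suffice?** The smallest margin with 90% power is (1.96 + 1.28) × SE: 4.52 points at 231 and 4.35 at 250. At M = 5 the size is 2 × (1.96 + 1.28)² × (15/5)² = 188.96, so 189 (190 with the unrounded quantile). At M = 4 it is 296 and at M = 3 it is 526, both above 250.

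**The case against.** The strongest reply is that this is a planning block. It sits in the sample-size section, the ENDPOINTS table footnotes its primary endpoints as being for sample size calculations, and d = 10 with N = 48 fits a margin of 10. On that view the hypotheses are loosely written inputs and the heading shows the intent. Against this, the section's own opening says that the hypotheses are to be proved, d is never called a margin, and N = 48 fits a difference test equally well. Even a pure planning block should not put one kind of test in its heading and another in its hypotheses.

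Other points have some force:

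- The absence of an analysis rule is not peculiar to AKS; ROM lacks one too. Only the conflict between heading and hypotheses is specific to AKS.
- The contrast between 2.5% and more than 99.9% depends on an assumed margin, which is why a range is shown.
- The block prints alpha = 0.025 beside a critical value indexed by 1 − alpha/2. Read literally as two-sided 0.025, that would need a critical value of 2.24 and N = 56. The printed 1.96 and N = 48 rule this out as the calculation used, but it is another reason to state the sidedness.
- ROM drives the trial size, and the sample-size heading calls AKS secondary. This limits the weight of the point but does not remove the contradiction.

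**Conclusion.** The concern holds. The AKS hypotheses are those of a superiority test under a non-inferiority heading, and nothing elsewhere in the plan repairs this. With truly equal knees and SD 15, the written test rejects 2.5% of the time one-sided (5% two-sided). The declared test would succeed more than 99.9% of the time at a margin of 10 and about 95% to 96% at a margin of 5, with 231 to 250 per group. These figures use a normal approximation and assumed margins; the contradiction itself needs no assumption.

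The plan should be corrected, but its size is not in question: N = 48 is unchanged at M = 10, and 250 per group governs for any margin of about 4.5 or more.

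Three smaller slips add no weight to this judgement. The 10 points are labelled as pain although the means and SD are on AKS. Beta = 0.10, the quantile 1.28 and N = 48 mean 90% power, while the label says 80%. And 1-year AKS is primary in the ENDPOINTS table but secondary in the sample-size heading.

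**What to change.** The sponsor should state which is wrong, the heading or the hypotheses.

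- **If non-inferiority is intended:** write H0: mu_t − mu_c ≤ −M against Ha: mu_t − mu_c > −M, and conclude non-inferiority if the lower limit of the two-sided 95% confidence interval for mu_t − mu_c lies above −M. State and justify M on the AKS scale (10 points, if that was the intention) and correct the pain label.
- **If a difference test is intended:** correct the heading, state whether the test is one- or two-sided, and check the opening sentence of the section that refers to non-inferiority methods.

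Keep the protocol's labels (trial = Vanguard Complete, control = High Flex RP). As a query only, ask the sponsor to confirm that direction, because STUDY OBJECTIVE words the comparison as High Flex to Vanguard Complete. In the same edit, restate the power as 90% and give 1-year AKS the same status in the ENDPOINTS table and the sample-size heading.

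**Cost.** Protocol wording and a short justification of M. At M = 10 the AKS size stays at 48 per group (51 after loss to follow-up). No patients, visits or data are added for any M of about 4.5 or more. A smaller margin would give less than 90% power with 231 analysed per group, and the AKS sample size would then have to be reconsidered.

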A PROSPECTIVE CONTROLLED MULTI-CENTER STUDY ON VANGUARD™ COMPLETE KNEE & VANGUARD™ HIGH FLEX RP KNEE

GENERAL INFORMATION

Principal Investigators

[name]., Ph.D. – 75 Cases
[name]., Ph.D. – 75 Cases
[name] [name]., Ph.D. – 75 Cases
[name]., Ph.D. – 75 Cases

Principal investigators are responsible for the overall project and performing the surgical procedures in all study groups. Responsible for applying for ethical and management approval, recruitment of patients, obtaining patient consent, managing postoperative care of patients and adverse event reporting.

Study Sponsor

Biomet Korea

Study sponsors take responsibility for initiation, management, and/or financing of a clinical studies at investigational sites.

Study Monitor in Korea

[name]

Study monitors are responsible for carrying out the monitoring procedure as indicated in the protocol.

STUDY OBJECTIVE

The primary objectives of this clinical study include:

- Evaluate size fit and long term performance of Vanguard Complete Knee (“Fixed”) System in Asian and Latino population Compare Vanguard High Flex Rotating Platform (“High Flex”) Knee System to Vanguard Complete Knee System in Asian population in terms of:
 - Early ROM
 - Clinical outcomes
- Compare current design to new design of Vanguard High Flex Rotating Platform Knee System in terms of :
 - Early ROM
 - Clinical outcomes

DEVICE DESCRIPTION

Vanguard Complete Knee

Vanguard Knee is a metal and polyethylene system designed to replace the body's natural knee joint and is indicated for cemented tibial and cementless femoral use. The system contains three (3) primary components and one (1) peripheral component. The primary components include, femoral, tibial, and bearing components, while the peripheral component is the patella button. The use of the patella button is optional.

Vanguard High Flex Rotating Platform Knee (current design)

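### Randomisation may be manual and no concealment is described, so surgeons who recruit and operate could learn the next arm before enrolling a patient

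*Combined protocol and SAP*

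**What the plan says.** The Randomization section is one paragraph and covers subgroup 2 only. On generation it says "The randomization will occur via a random number generator (manual or computer". On assignment it says that, for patients who meet the inclusion criteria, "randomization will occur by retrieving the next randomly generated group assignment". The ratio is 1:1: "Patients have an equal opportunity of being assigned to the trial group or control group". One safeguard is stated: "The doctor or other health care professional does not choose the participants for each group".

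Other sections set the context:

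- **General Information.** The principal investigators are responsible for "performing the surgical procedures in all study groups". The same paragraph continues: "Responsible for applying for ethical and management approval, recruitment of patients, obtaining patient consent".
- **Patient Selection.** Beyond the indications, there are selection factors to weigh, such as willingness to follow instructions and nutritional state, and a list of relative contraindications.
- **Institutions.** "There will be a maximum of 8 sites from Korea and Japan in subgroup 2".
- **Endpoints.** ROM at 1 year is a primary endpoint.
- **Radiographic Protocol.** Each investigator reads his own patients' films. No blinding is described anywhere.
- **Data Collection and Confidentiality.** All sites already enter data in one online database with user authentication and restricted access.

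No section names a holder of the sequence, central or web release, sealed envelopes, blocking or stratification.

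**The concern.** Randomisation protects the comparison only if the person deciding whether to enrol a patient cannot know the next arm. The stated safeguard stops a clinician from choosing the arm openly. It does not stop someone who can see the next assignment from deciding whom to approach, or when.

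The exposure is real in this trial. The recruiting surgeon is also the operating surgeon, and can defer or decline a patient on judgement-based criteria without breaching the protocol. The Device Description supplies a possible motive: the High Flex knee is meant for patients who need flexion beyond 135 degrees, and its full range is expected only where the patient had similar flexion before surgery. Steering good flexors towards that implant would act directly on 1-year ROM. Without blinding, concealment is the main protection available. The High Flex arm is also the control for subgroup 4, so a bias here would carry into that comparison.

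**Working it through.** **1. What the text settles and what it leaves open**

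| Question | Text |
|---|---|
| Generator | Random numbers, manual or computer |
| Assignment step | The next assignment is retrieved |
| Trigger | Inclusion criteria met; consent is a pre-operative item in the data-collection table but is not tied to release |
| Who holds or sees the assignments | Not stated |
| Blocks or strata | Not stated |

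The first two rows are choices the plan makes. They permit a hand-made sequence kept at the site.

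**2. The plan's own figure, for scale only**

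Inputs from the sample-size section: d = 5, SD = 17.5, alpha = 0.025, power 80%. Taking alpha as two-sided:

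n = 2 × [(2.241 + 0.842) × 17.5 / 5]² = 232.9, so 233 per group against the stated 231 (0.9% apart).

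This point does not dispute that figure, and the agreement is no evidence for the point. With 250 per group, the standard error of the ROM difference is 17.5 × √(2/250) = 1.57 degrees.

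**3. Possible bias from steering**

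Bias = share of allocations steered × pre-operative ROM gap between the patients exchanged × slope of 1-year ROM on pre-operative ROM. None of the three inputs is in the documents. The assumed ranges are 2-10%, 10-20 degrees and 0.3-0.5.

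- Low end: 0.02 × 10 × 0.3 = 0.06 degrees (1% of d).
- High end: 0.10 × 20 × 0.5 = 1.0 degree (20% of d).

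**4. Chance imbalance between sites**

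Assume unrestricted 1:1 randomisation and 8 equal sites of 62 knees (500/8 = 62.5).

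- The median of the largest within-site difference is 14 knees. The probability that some site differs by 16 or more is 0.37.
- With 75 cases per surgeon, as General Information lists for four investigators, a 45:30 split or worse has probability 10.5% for any one surgeon.
- Effect on ROM: if site means vary with SD τ, the arm difference shifts by a random amount with mean 0 and SD τ × √[(1 − 1/8) × 4/496]. For τ = 3 this is 0.25 degrees; for τ = 5 it is 0.42 degrees (τ assumed). The standard error is 1.57.
- Adjusting for site multiplies the standard error by about √(1 − ICC). At an assumed ICC of 0.02-0.10 this is 0.99-0.95, a gain of 1-5%.
- Power at a 228:272 split, the 95% limits for 500 knees, is 82.7%, against 83.0% at 250:250.

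**5. Predictability of small blocks**

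A surgeon who tracks past implants and always guesses the arm with fewer so far is right, per block of size 2m, on average m + ½ × [4^m / C(2m, m) − 1] times.

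- Blocks of 4: 2 + ½ × (16/6 − 1) = 2.83 of 4, or 71%.
- Blocks of 6: 3 + ½ × (64/20 − 1) = 4.10 of 6, or 68%.
- An equal mix of the two: (2.83 + 4.10)/10 = 69%.

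The rule does not need the block size, so mixing 4s and 6s does not defeat it. Concealed unrestricted randomisation gives 50%.

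**The case against.** The strongest reply is that this is silence, not a stated flaw. A reader might infer that the plan uses a simple list without concealment, so that allocation can be foreseen. The documents do not support that. They never use the words simple, list or unconcealed, and retrieving the next assignment also fits on-demand generation, where there is nothing to look ahead at. The fixed target of 250 knees per arm may point to restricted randomisation: unrestricted allocation of 500 gives exactly 250:250 with probability only 3.6%, although the 250s may be targets. Eligibility comes before assignment, and the safeguard sentence can be read as covering which patient goes to which arm. This much stands: foreseeability depends on the sequence being visible, and the fault is that the text allows it to be.

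A reader might also infer that device is partly confounded with surgeon. That does not hold. Chance imbalance has zero expected bias, the ordinary standard error covers it, and its effect is small (steps 4 of the working). The count of 14 knees also depends on assuming unrestricted randomisation and 8 equal sites, whereas 8 is a maximum.

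The steering inputs are invented and their upper end is generous; that objection stands too. So does the warning that small blocks within surgeon would bring back some of the predictability at issue.

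None of this answers the central point. Manual generation is expressly allowed, no concealment is described, and the people who could exploit foreknowledge are those who enrol and operate.

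**Conclusion.** The point holds in a limited form. The procedure as written permits a manual sequence held where the recruiting surgeon can see it, and nothing elsewhere in the document closes that gap. This goes beyond missing detail, because the plan actively allows manual generation and a safer procedure is available with tools it already has. It is not evidence that allocation will be foreseen.

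The size of any bias cannot be derived from the documents. The range of 0.06-1.0 degrees (1-20% of d) rests wholly on the assumed steering share, ROM gap and slope. Chance imbalance between sites adds noise of about 0.25-0.42 degrees if site means vary with SD 3-5 degrees. It adds no systematic bias and barely affects power. This is a cheap improvement that should be made; it does not change the 231 or 250 per group.

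**What to change.** In the Randomization section:

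1. Delete the manual option and state that the sequence is computer-generated.
2. State that it is held centrally, away from the sites, and name the role that holds it.
3. State that assignments are released one patient at a time through the existing online database, only after eligibility and consent have been recorded there.

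In the analysis of 1-year ROM, include site as a factor. This removes the effect of chance site imbalance for a small gain in precision.

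Stratifying by site is optional. If it is used, prefer large blocks of varying, undisclosed size, because small blocks within surgeon are partly predictable when the operating surgeon knows every past implant (about 69% correct guesses with blocks of 4 or 6).

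The cost is a one-time set-up in the database, a few sentences of protocol text and a short step before each operation. The sample size is unchanged.
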